## PROTOCOL SYNOPSIS

Study Title	Enhancing Caregiver-Infant Communication to Prevent Obesity
Funder	Eunice Kennedy Shriver National Institute of Child Health and Human Development
Clinical Phase	Stage 1 for Behavioral Intervention Development
Study Rationale	
Once obese as an infant, the relative risk of remaining obese appears to rise with increasing age. Thus, the early years of life have been posited as an important target period for obesity prevention. Widely viewed as a response to genetic, interpersonal, and environmental factors, obesity fundamentally reflects an imbalance between energy intake and expenditure. Self-regulation of energy intake aligned with physiologic need is essential to this balance. The process(es) by which infants begin to disassociate eating behavior from physiologic need is unclear, thus it is crucial to better understand predictors of individual differences in self-regulation of energy intake.
 
A chronic mismatch between a caregiver's feeding behavior and the infant's state (feeding in the absence of hunger and/or feeding beyond fullness), is thought to contribute to obesity by undermining the infant's capacity to self-regulate intake; the current proposal will be the first to examine the effects on autonomic regulation.

Study Objective(s)	
Primary Outcome
 
To evaluate the initial impact of the intervention. We expect the following for the experimental group:
 
Infants will have more optimal growth (weight-for-length Z scores closer to 50th %) than the control group by T3.
 
Secondary Outcome
 
To evaluate the initial impact of the intervention. We expect the following for the experimental group:
 

○ Infants will have enhanced self-regulation of energy intake (closer to estimated energy requirements) than the control group by T3.

 
Tertiary Outcomes
 
To evaluate the initial impact of the intervention. We expect the following for the experimental group:
 

○ A) Dyads will demonstrate (1) improvement in observed feeding responsiveness and (2) higher observed feeding responsiveness than the control group by T3 (6-months post-baseline).

○ B) Mothers will (1) perceive higher infant satiety responsiveness and (2) report more responsiveness

---

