**Study Phases**  
**Screening**

Screening: screening for eligibility and obtaining consent

---

Study Treatment Follow-Up	Study Treatment: study intervention/experimental treatment from baseline visit (T1) monthly until 3-months post-baseline (T2) Follow-up: 6-months post-baseline (T3)
Efficacy Evaluations	Primary efficacy evaluation measures: 
 
1. Infants in the intervention group will have more optimal growth (weight-for-length Z scores closer to 50th %) than the control group by T3.
 

Pharmacokinetic Evaluations	N/A
Safety Evaluations	
 
• Assessment of self-reported health of parent and infant prior to data collection
 
• Monitoring of parent's and infant's responses during intervention and data collection
 
• Reports of adverse events
 

Statistical And Analytic Plan	To evaluate the initial impact of the intervention longitudinally for each maternal and infant outcome listed in the primary, secondary, and first two tertiary outcomes above, we will fit separate linear mixed-effects random coefficients models. These will model the linear trajectories of the group-specific means across all available time points using the actually observed timing. The initial impact of the intervention will be formally assessed through a statistical hypothesis test of model parameter representing the difference in these slopes. More specifically, these models will include terms for the intervention group (as an indicator variable), actual time of data collection (as continuous weeks from baseline), and their interaction. Covariates identified above to correct for imbalance will be included, as well as the factors stratified in the randomization, and the models will account for the repeated measures correlation structure. Statistical contrasts will also be constructed to estimate and test the changes over time separate for each group.

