#### **Study Phases:**

Screening: screening for eligibility and obtaining consent

Study Treatment: study intervention/experimental treatment from baseline visit (T1: age 4-9-months) monthly until 3-months post-baseline (T2: age 7-12-months)

Follow-up: 6-months post-baseline (T3: age 10-15-months)

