### **6.3 Statistical Methods**

Descriptive statistics will be calculated for each measure (see Aims 2 & 3 in Table of Measures, Section 5) at each time point by group. All analyses will be conducted using an intention-to-treat approach.

Preliminary analyses will be conducted to determine whether, despite randomization, the intervention and control groups exhibit a random imbalance at baseline on any measured variable. If important imbalances are found, the corresponding variable will be considered as a covariate in subsequent models to statistically correct for the imbalance. To evaluate the initial impact of the intervention longitudinally for each maternal and infant outcome listed above as primary, secondary, and the first two tertiary outcomes (i.e., more optimal growth, indicators of enhanced self-regulation of energy intake [NDS-R data compared to age- and sex-specific estimated energy requirements], reported infant feeding behavior and maternal feeding behaviors/beliefs, and observed dyadic feeding responsiveness), we will fit separate linear mixed-effects models. These could include a random coefficients model to examine the linear trajectories of the group-specific means across all available time points using the actually observed timing. The initial impact of the intervention will be formally assessed through a statistical hypothesis test of model parameter representing the difference in these slopes. More specifically, these models will include terms for the intervention group (as an indicator variable), actual time of data collection (as continuous weeks from baseline), and their interaction. An alternative modeling strategy would be to utilize mixed-effects model in a repeated measures context to examine the trajectories of the group-specific means across all available time points using the visit timepoint; these models will include terms for the intervention group (as an indicator variable), visit timepoint (as one or more indicators to reflect this categorical variable), and their interaction term(s). In this scenario, the initial impact of the intervention will be formally assessed through a statistical hypothesis test of linear contrasts of model parameters representing the between-group difference at each timepoint. Covariates identified above to correct for imbalance will be considered for inclusion in these models, as well as the factors stratified in the randomization, and the models will account for the repeated measures correlation structure. Statistical contrasts will also be constructed to estimate and test the changes over time separately for each intervention group. As useful information for planning subsequent studies, effect sizes for each measure will be calculated for each follow-up time point as the ratio of the mean difference between the intervention and the control groups to its standard deviation, as well as the producing the estimated correlation matrices across the repeated measures.

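### Tertiary hypothesis A(1) counts improvement within the experimental arm as an expected impact, and the only test of it on its own ignores the control group

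*Combined protocol and SAP*

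**What the plan says.** The Protocol Synopsis introduces the tertiary outcomes with "To evaluate the initial impact of the intervention. We expect the following for the experimental group". Outcome A then has two numbered parts: "Dyads will demonstrate (1) improvement in observed feeding responsiveness and (2) higher observed feeding responsiveness than the control group by T3". Part (2) names the control group; part (1) does not.

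Section 6.3 gives the formal test of impact in two alternative forms, both between-group. In the random coefficients model, impact is "formally assessed through a statistical hypothesis test of model parameter representing the difference in these slopes". In the categorical-time model it rests on "linear contrasts of model parameters representing the between-group difference at each timepoint". Section 6.3 applies these to the primary, secondary and first two tertiary outcomes, and names observed dyadic feeding responsiveness among them.

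Section 6.3 then adds: "Statistical contrasts will also be constructed to estimate and test the changes over time separately for each intervention group". The Statistical and Analytic Plan row of the synopsis has the same provision: "Statistical contrasts will also be constructed to estimate and test the changes over time separate for each group". Neither place says what these tests are for, and neither calls them descriptive.

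On timing, section 3.1 (Study Phases) gives "T1: age 4-9-months" for baseline and "Follow-up: 6-months post-baseline (T3: age 10-15-months") for the last visit.

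**The concern.** Because A(2) is the comparison with control, A(1) can only mean change within the experimental arm. It is listed as an expected impact in its own right, and the within-arm contrasts are the only planned analysis that tests it on its own. Over six months at this age, change in that arm can come from the intervention, from the infant's development, or from a dyad growing used to being filmed at home for the second and third time. A within-arm test cannot separate these. The trial has a randomised control group that can, and A(1) does not use it.

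The plan itself treats development as relevant: section 3.2 stratifies randomisation by age group for that reason. The outcome is a dyadic score drawn from both infant and mother (section 5 table), so infant development could move it. If A(1) were reported as met on its own p-value, a listed impact would be claimed without evidence that the intervention caused it. Section 13 plans to publish the tertiary outcomes.

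**Working it through.** **Inputs.** From section 6.4: 32 complete dyads per group (40 less 20% attrition), first-order autoregressive correlation with parameter 0.9, a linear difference of 0.4 SD by T3, one-sided .05, stated power above .86. Section 6.3 states no significance level, so I use the one in 6.4. The common change from T1 to T3 (drift) is my assumption, because the documents give none.

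**The plan's own figure first.** The T1-T3 correlation is 0.9² = 0.81. The SD of the T1-T3 change is √(2 × (1 − 0.81)) = 0.616 SD.

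- Unadjusted between-group test of change: SE = 0.616 × √(2/32) = 0.154; 0.4/0.154 = 2.60; power 0.829 (0.822 by noncentral t).
- Adjusted for baseline: residual SD = √(1 − 0.81²) = 0.586; SE = 0.147; 0.4/0.147 = 2.73; power 0.861.
- 32 complete dyads plus 8 per arm with T1 and T2 only: power 0.866.

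The stated figure therefore reproduces if the test adjusts for baseline or counts the partial data, and section 6.4 does mention incomplete data. The inputs are usable for what follows.

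**Within-arm test when the intervention does nothing.** Let both arms drift upward by d SD from T1 to T3. In the experimental arm SE = 0.616/√32 = 0.109. The test statistic is noncentral t with 31 df and noncentrality d/0.109, and improvement is declared above the upper 5% point of t with 31 df. With a T1-T3 correlation of 0.5 the SD of change is √(2 × 0.5) = 1 and SE = 1/√32 = 0.177.

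| Upward drift d | d/0.109 | Correlation 0.81, one-sided .05 | Correlation 0.5, one-sided .05 | Correlation 0.81, two-sided .05 (upper tail) |
|---|---|---|---|---|
| 0 | 0 | 5% | 5% | 2.5% |
| 0.1 SD | 0.92 | 23% | 14% | 14% |
| 0.2 SD | 1.83 | 56% | 30% | 43% |
| 0.3 SD | 2.75 | 85% | 51% | 76% |

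If drift is downward the noncentrality is negative and the one-sided rate falls below 5%.

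**Between-arm test under the same conditions.** A drift common to both arms cancels. A simulation of 40,000 trials at correlation 0.81 gave rejection rates of 5.2%, 5.2% and 5.1% at drifts of 0, 0.2 and 0.4 SD. The within-arm test in the same simulation rejected in 5.1%, 56.4% and 97.5%.

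**Cost in power.** Judging outcome A between groups uses a test that is already planned. Its power for 0.4 SD is the 0.83 to 0.87 shown above, with no extra dyads.

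**The case against.** A reader might infer that the plan offers within-arm tests in general as evidence of impact. The documents do not support that. Section 6.3 twice ties the formal assessment of impact to between-group parameters, observed feeding responsiveness included, and section 6.4 powers only the between-group comparison. The within-arm contrasts are an addition with no stated inferential role. Nor does the plan propose to compare the two arms' p-values; it specifies a group-by-time interaction, which is the right alternative. The objectives in section 2 are all against control.

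A reader might also infer that a useless intervention would often appear to work. That does not follow either. A(1) and A(2) are joined by *and*. If both must hold, the joint claim cannot succeed more often than the controlled part, whose test of change stays near 5% under the null. The larger percentages apply only if A(1) is reported as impact without A(2), and nothing in the plan says it will be. They also need upward drift. The documents do not show that the responsiveness score rises with age, and section 4.2 lists fear of new foods among the developments to be discussed with mothers, so the direction is open.

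Maturation also bears less on the primary outcome, a weight-for-length Z score, and on the secondary outcome, intake against age- and sex-specific requirements, because both are already referenced to a standard.

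All of this stands and narrows the point. What remains is that A(1) is numbered separately, sits under the impact heading, has no comparator, and is matched by a test that no section labels descriptive.

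**Conclusion.** The point holds for A(1) and for the unlabelled within-arm tests, and no further. A significant within-arm improvement would not show that the intervention worked. How often it would arise with no effect depends on drift: 5% at none, 23% to 85% for 0.1 to 0.3 SD upward at the plan's assumed correlation, 14% to 51% at a correlation of 0.5, and below 5% if drift is downward. These figures rest on 32 dyads, a one-sided .05 level and my assumed range of drift; the documents give neither its size nor its direction.

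Severity is modest: this is a tertiary outcome in a Stage 1 behavioural study, and the valid between-group test is already planned. The change is one to consider rather than a condition for the analysis to stand.

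**What to change.** 1. In the synopsis, reword A(1) as a greater improvement than control on the observed responsiveness score, or drop it and keep A(2).
2. In section 6.3 and the Statistical and Analytic Plan row of the synopsis, report the change within each group as an estimate with a 95% confidence interval, labelled descriptive, in place of a test.
3. In both places, add that impact is judged only on the between-group contrast.

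The cost is a few sentences of wording. No dyads, visits or estimates are lost; within-arm p-values are no longer reported as evidence of impact.

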obesity prevention during infancy has become a priority for research. Research in this area is relatively new and results have been mixed regarding measures of obesity. Obesity intervention components have included: teaching caregivers strategies for improving infant sleep quality/duration, increasing infant physical activity, providing nutritional education to support breastfeeding, increasing food variety, appropriate timing of complementary food introduction, and increased responsiveness to infant hunger and satiety cues. These studies report improvements in several factors that have been associated with obesity risk, including: improved infant sleep, less TV exposure, decreased sweet/juice intake, delayed introduction of solids, increased breastfeeding duration and/or rates, and increased parental responsiveness (self-reported) to infant hunger and satiety cues. Most studies have failed to impact significantly body mass index (BMI) or Weight/Length. Two have found a decrease in either weight for length % or BMI while two other studies have noted an increase in weight and length or BMI. While impact on BMI or Weight/Length appears equivocal, it is quite possible that effects on obesity status and growth will become evident later in development; most of the studies reported outcomes < 6 months after delivery of the last intervention component. Of importance regarding safety, none of the intervention studies demonstrated concerning weight loss or growth delay. While the etiology of obesity is considered multifactorial, it arises fundamentally through an imbalance in energy intake and output. The aforementioned studies used multi-focal intervention components, yet there was little focus on the assessment of support for energy intake self-regulation and no focus on evidence of self-regulation (eating behavior responsive to physiologic state [i.e., hungry or satiated]). Several studies included efforts to increase caregiver responsiveness to infant hunger and satiety cues, which is thought to support self-regulation, yet only one investigative team has reported improvement in parental responsiveness (self-reported). In short-term protocols (meal to meal), infants have demonstrated the ability to self-regulate energy intake over days and weeks, through compensation or adjustment for variations in the energy content of food. This self-regulatory capacity appears to increasingly diminish in the years following toddlerhood, at least in short-term protocols. Thus, it has been suggested that the first 2 years of life may be a critical period for the development of self-regulation of intake.

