### **3.3 Study Duration, Enrollment and Number of Subjects**

We plan for 80 parent-infant dyads (160 subjects) randomized to invention (40 dyads) or control (usual care; 40 dyads). Length of participation will be 6-6.5 months and planned study duration is 2 years.

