
**6.4 Sample Size and Power:** Dyads will be randomized to either the intervention ( $n = 40$ ) or the control ( $n = 40$ ) group. Conservatively, a 20% attrition rate will be assumed, though less attrition will result in greater statistical power. Hence, we assume two-group, longitudinal comparisons of complete data on 32 dyads per group, as well as incomplete data (at some, but not all, time points), for analyses of each measure. Power calculations are performed with the POWERLIB20 SAS/IML module, which incorporates methods to calculate power for the general linear multivariate model, which is closely related to the general linear mixed model, assuming a first-order autoregressive correlation structure across the repeated measures with parameter  $\rho=0.9$ . We intend to estimate the power for the initial impact of the intervention through a test of mean linear change between the two groups across the three timepoints for each maternal and infant outcome in Aim 2 in separate multivariate models. The study will be well-powered to detect moderate changes in slope across the group trajectories over time. A linear difference of .4 SD by T3 with 32 dyads per group will provide statistical power exceeding .86 at the one-sided .05 significance level.

**6.5 Interim Analysis:** N/A

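### Section 6.4: with 32 complete dyads per group, the described test has one-sided power of about .82; the assumption that lifts it to .86 is not stated

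*Combined protocol and SAP*

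**What the plan says.** Section 6.4 (Sample Size and Power) gives the plan's only power figure: "A linear difference of .4 SD by T3 with 32 dyads per group will provide statistical power exceeding .86 at the one-sided .05" level. The inputs stand in the same paragraph:

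- 40 dyads per group are randomized and 20% attrition is assumed, which leaves 32.
- The correlation is set by "assuming a first-order autoregressive correlation structure across the repeated measures with parameter" 0.9.
- The powered test compares mean linear change between the groups over the three timepoints.
- The analysis set is described as "complete data on 32 dyads per group, as well as incomplete data (at some, but not all, time points"). The amount and pattern of the incomplete data are not given.

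Section 3.3 confirms 1:1 allocation ("randomized to invention (40 dyads) or control (usual care; 40 dyads"). Section 3.1 places T1 at baseline, T2 at 3 months and T3 at 6 months. Section 6.3 specifies mixed models with group, time and their interaction. Baseline variables enter as covariates only if an important imbalance is found.

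**The concern.** The inputs are complete enough for a reader to recompute the power, and the natural calculation falls about 4 points short of the stated figure. On this one number 6.4 rests its description of the study as well powered. At .822 the chance of missing the target effect is 1 − .822 = .178, against less than .14 implied by the text. A future reader, or the planner of the larger study that section 1.3 mentions, would take .86 as the power of 32 complete dyads per group.

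**Working it through.** **Inputs.** From 6.4: difference 0.4 SD by T3, growing linearly (0, 0.2, 0.4); n = 32 per group; AR(1) with ρ = 0.9, so corr(T1, T3) = 0.9² = 0.81; one-sided α = .05. From 3.1: visits at 0, 3 and 6 months.

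**Trying to reproduce .86 with 32 complete dyads per group**

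1. For three equally spaced visits the linear contrast has weights (−1, 0, 1), i.e. T3 − T1.
2. Var(T3 − T1) = 2(1 − 0.81) = 0.38 SD². The generalized least squares slope under AR(1) has weights (−.5, 0, .5) and variance .095 per 3-month step. Over two steps that is 4 × .095 = 0.38, so the slope model gives the same answer.
3. SE of the group difference = √(0.38 × 2/32) = 0.154.
4. Noncentrality = 0.4/√(0.38 × 2/32) = 2.596.
5. Exact power (noncentral t, 62 df) = .822. Normal approximation: Φ(2.596 − 1.645) = Φ(0.951) = .829. A simulation of 100,000 trials gave .821.

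The stated figure is not reproduced on this reading.

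**What would produce about .86 (one-sided .05)**

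| Reading | Noncentrality | Power, exact t | Power, normal |
|---|---|---|---|
| 32 complete per group, as described | 2.596 | .822 | .829 |
| 32 complete + 4 per group with T1 and T2 | 2.675 | .842 | .849 |
| 32 complete + all 8 per group with T1 and T2 | 2.752 | .859 (62 df) to .861 (78 df) | .866 |
| Baseline-adjusted T3 comparison, 32 per group | 2.728 | .854 | .861 |
| 36 complete per group | 2.753 | .860 | .866 |

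The rows with 4 or 8 partial dyads use the slope model with separate group intercepts. The residual variance in the baseline-adjusted row is 1 − 0.81² = 0.3439. Thirty-six complete dyads would mean 10% attrition (36/40), not the 20% assumed.

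**Detectable difference.** Holding n = 32 and all else fixed, exact power is .853 at 0.42 SD and .868 at 0.43 SD. Power of .86 therefore corresponds to about 0.425 SD.

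**Readings that do not match either.** All 40 per group complete gives .891. Compound symmetry at 0.9 gives .971. A comparison at T3 alone gives .475. The 2-df group-by-visit test gives .61 at .05 or .73 at .10.

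**The case against.** The strongest defence is that 6.4 does not limit itself to complete cases: it expects partial data as well, and a mixed model would use them. If every assumed dropout were seen at both T1 and T2, power would be .859 to .861, essentially the stated figure. A baseline-adjusted analysis at 32 per group would also come close (.854, or .861 by the normal approximation). This defence stands to the extent that .86 cannot be called impossible or a demonstrated slip. It does not make the sentence reproducible. The amount of partial data is not given, all 8 per group is the most favourable case, and the power sentence itself names only 32 dyads. The multivariate model named in 6.4 ordinarily takes complete response vectors. Baseline adjustment is not part of the test that 6.4 describes, and 6.3 makes covariates conditional on observed imbalance.

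It can also be said that little turns on it in an exploratory, developmental study: .82 is still reasonable power and the detectable difference moves only from 0.40 to 0.425 SD. That is fair, and it is why the remedy is confined to wording.

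A reader might go further and infer that the true power is .72, because the same inputs give .724 when tested two-sided at .05. The documents do not support calling that a discrepancy: 6.4 claims power only "at the one-sided .05 significance level". A reader might also infer that no direction can be defended, since section 1.3 cites two studies with decreases in weight for length or BMI, "while two other studies have noted an increase in weight and length" or BMI. Those are signed changes in size. The hypothesis in 2.1 concerns closeness to the median, which is directional when scored as distance from it. Nor does the power paragraph show that an adverse shift would go unseen: 6.3 plans group-specific change estimates and effect sizes at each follow-up. Whether the primary test should be two-sided is a design choice, separate from this arithmetic.

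**Conclusion.** The point holds as one of reproducibility. For the test and inputs in 6.4, 32 complete dyads per group give one-sided power of about .82, a shortfall of roughly 4 points (.86 − .822 = .038), or 3 points by the normal approximation. About .86 is reachable only with something 6.4 leaves unsaid: near-complete T1 and T2 data from all 8 dropouts per group, or about 36 complete dyads per group. Baseline adjustment comes close at .854.

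This rests on equal visit spacing, the stated AR(1) correlation of 0.9, equal variances across visits and groups, and reading the linear difference as zero at T1 and 0.4 SD at T3. The partial-data rows further assume that dropouts are seen at T1 and T2 and missed only at T3. The stronger conclusion, that .86 is simply a miscalculation, is not supported, because the documents do not show which partial-data or adjustment assumption was entered.

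**What to change.** Restate the last sentence of 6.4 along these lines: power is about .82 at one-sided .05 for a 0.4 SD linear difference by T3 with 32 complete dyads per group and AR(1) 0.9, rising to about .86 if all assumed dropouts contribute T1 and T2. Alternatively, keep .86 and name the partial-data pattern, baseline adjustment or number of dyads that produces it.

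Keep 80 dyads. The cost is a change of wording and a slightly less favourable figure; no design element, endpoint or analysis changes. For information only, the same inputs give .72 if the test is run two-sided at .05.
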